## **12 STUDY MONITORING**

### **12.1 Responsibilities of the investigator(s)**

The Investigator(s) undertake(s) to perform the Clinical Trial in accordance with this Clinical Trial Protocol, ICH guidelines for Good Clinical Practice and the applicable regulatory requirements.

The Investigator is required to ensure compliance with all procedures required by the Clinical Trial Protocol and with all study procedures provided by the Sponsor (including security rules). The Investigator agrees to provide reliable data and all information requested by the Clinical

Trial Protocol (with the help of the Case Report Form [CRF], Discrepancy Resolution Form [DRF] or other appropriate instrument) in an accurate and legible manner according to the instructions provided and to ensure direct access to source documents by Sponsor representatives.

The Investigator may appoint such other individuals as he/she may deem appropriate as Sub-Investigators to assist in the conduct of the Clinical Trial in accordance with the Clinical Trial Protocol. All Sub-Investigators shall be appointed and listed in a timely manner. The Sub-Investigators will be supervised by and under the responsibility of the Investigator. The Investigator will provide them with a copy of the Clinical Trial Protocol and all necessary information.

The Sponsor of this Clinical Trial is responsible to Health Authorities for taking all reasonable steps to ensure the proper conduct of the Clinical Trial Protocol as regards ethics, Clinical Trial Protocol compliance, and integrity and validity of the data recorded on the Case Report Forms. Thus, the main duty of the Monitoring Team is to help the Investigator and the Sponsor maintain a high level of ethical, scientific, technical and regulatory quality in all aspects of the Clinical Trial.

At regular intervals during the Clinical Trial, the site will be contacted, through monitoring visits, letters or telephone calls, by a representative of the Monitoring Team to review study progress, Investigator and patient compliance with Clinical Trial Protocol requirements and any emergent problems. During these monitoring visits, the following, but not exhaustive, points will be scrutinized with the Investigator: patient informed consent, patient recruitment and follow-up, Serious Adverse Event documentation and reporting, Investigational Product allocation, patient compliance with the Investigational Product regimen, Investigational Product accountability, concomitant therapy use and quality of data.

### **12.2 Source document requirements**

According to the ICH guidelines for Good Clinical Practice, the Monitoring Team must check the Case Report Form entries against the source documents, except for the pre- identified

source data directly recorded in the Case Report Form. The Informed Consent Form will include a statement by which the patient allows the Sponsor's duly authorized personnel, the Ethics Committee (IRS/IEC), and the regulatory authorities to have direct access to source data which support the data on the Case Report Forms (e.g., patient's medical file, appointment books, original laboratory records, etc.). Such personnel, bound by professional secrecy, must keep confidential all personal identity or personal medical information (according to confidentiality rules).

### **12.3 Use and completion of Case Report Forms(CRFS) and additional requests**

It is the responsibility of the Investigator to maintain adequate and accurate CRFs (according to the technology used) designed by the Sponsor to record (according to the Sponsor's instructions) all observations and other data pertinent to the clinical investigation. All CRFs should be completed in their entirety in a neat, legible manner to ensure accurate interpretation of data.

Should a correction be made, the information to be modified must not be overwritten. The corrected information will be transcribed by the authorized person next to the previous value, initialed and dated.

The CRFs will be faxed (data fax system) visit per visit or collected at each routine monitoring visit.

The computerized handling of the data by the Sponsor after receipt of the CRFs may generate additional requests (ORF) to which the Investigator is obliged to respond by confirming or modifying the data questioned. The requests with their responses will be appended to the CRFs held by the Investigator and the Sponsor.

### **12.4 Use of computerized systems**

Computerized systems will be used to create, modify, maintain, archive, retrieve and transmit data (IVRS, monitoring tool, data entry and statistical analysis).

---

### **13 PUBLICATION OF RESEARCH FINDINGS**

Publication of the results of this trial will be governed by the policies and procedures developed by the Executive Committee. The trial results will be published as soon as possible after database lockdown.

This trial will produce detailed data on treatment effects, medical care, and outcomes in a cohort of 5100 subjects with TIA or minor ischemic stroke. CHANCE biostatisticians will be consulted to assure that it is impossible to uniquely identify any participant. This may mean removing or categorizing certain variables. A data use agreement will not be required for access to this dataset. Diskettes with the data in comma-delimited text format will be sent to parties that express interest, including a data dictionary in a text file.

### **14 ANCILLARY STUDIES**

Proposals for ancillary studies will be reviewed by the Executive Committee. Sites will not be required to participate in any ancillary study that requires additional data collection, but they will be encouraged to participate in accepted studies. Publication of the results of these studies will be governed by the policies and procedures developed by the Executive Committee.

---

## **16 APPENDIXS**

### *Appendix 1: Definition of End Points*

Stroke	Sudden symptoms and signs of focal disturbance of cerebral function associated with cerebral circulation disorders. Etiology would be classified based on SSS-TOAST standard.
Ischemic stroke	An acute focal infarction of the brain or retina. Criteria: (1) acute onset of a new focal neurological deficit with clinical or imaging evidence of infarction lasting more than

	
24 hours and not attributable to a non-ischemic etiology (not associated with brain infection, trauma, tumor, seizure, severe metabolic disease, or degenerative neurological disease); or (2) acute onset of a new focal neurological deficit and not attributable to a non-ischemic etiology lasting less than 24 hours, but accompanied by neuroimaging evidence of new brain infarction; or, (3) rapid worsening of an existing focal neurological deficit lasting more than 24 hours and not attributable to a non-ischemic etiology, and accompanied by new ischemic changes on brain MRI or CT, and clearly distinct from the index ischemic event.

Hemorrhagic stroke
	
An acute extravasation of blood into the brain parenchyma or subarachnoid space with associated neurological symptoms.

TIA
	
A neurological deficit of sudden onset, resolving completely, attributed to focal brain or retinal ischemia without evidence of associated acute focal infarction of the brain. Criteria: rapid onset of a focal neurological deficit that is without evidence of acute focal infarction of the brain, and is not attributable to a non-ischemic etiology (brain infection, trauma, tumor, seizure, severe metabolic disease, or degenerative neurological disease)

Symptomatic intracerebral hemorrhage
	
Any extravascular blood in the brain associated with clinical deterioration, as defined by an increase of 4 points or more in the score on the NIHSS, or that led to death and that was identified as the predominant cause of the neurologic deterioration. Intracerebral hemorrhage is defined as an acute extravasation of blood into the brain parenchyma. Criteria: evidence of hemorrhage in the brain parenchyma demonstrated by head imaging, surgery, or autopsy


Asymptomatic intracerebral hemorrhage
	
an acute extravasation of blood into the brain parenchyma without clinical deterioration. Criteria: evidence of hemorrhage in the brain parenchyma demonstrated by head imaging, surgery or autopsy

Other symptomatic intracranial hemorrhage
	
Any extravascular blood within the cranium associated with clinical deterioration, as defined by an increase of 4 points or more in the score on the NIHSS, or that led to death and that was identified as the predominant cause of the neurologic deterioration. Other Intracranial Hemorrhage is defined as an acute extravasation of blood into the subarachnoid space, epidural space, or subdural space with associated symptoms. Criteria: evidence of hemorrhage in the subarachnoid space, epidural space, or subdural space demonstrated by head imaging, surgery, or autopsy

Other Asymptomatic intracranial hemorrhage
	
An acute extravasation of blood into the subarachnoid space, epidural space, or subdural space without associated symptoms. Criteria: evidence of hemorrhage in the subarachnoid space, epidural space, or subdural space demonstrated by head imaging, surgery, or autopsy

Myocardial infarction with coronary revascularization
	
Evidence of myocardial necrosis in a clinical setting consistent with myocardial ischemia, treated with coronary revascularization. Criteria: The diagnosis of MI will be based on an algorithm developed from the Universal Definition of Myocardial Infarction (Circulation 2007 116:2634-2653) that takes into account 5 categories of clinical information from the acute event: rise and/or fall of cardiac biomarkers, ECG abnormalities, clinical setting, imaging evidence, and pathology.

Myocardial infarction without coronary
	
Evidence of myocardial necrosis in a clinical setting consistent with myocardial ischemia, not treated with

revascularization	coronary revascularization. Criteria: The diagnosis of MI will be based on an algorithm developed from the Universal Definition of Myocardial Infarction (Circulation 2007 116:2634-2653) that takes into account 5 categories of clinical information from the acute event: rise and/or fall of cardiac biomarkers, ECG abnormalities, clinical setting, imaging evidence, and pathology.
Coronary Revascularization without myocardial infarction	A procedure to improve coronary blood flow for documented coronary artery disease, but with no documentation of myocardial infarction. Criteria: Documented coronary angioplasty, stenting, or bypass surgery for demonstrated or presumed coronary artery disease
Ischemic vascular death	Death due to ischemic stroke, myocardial infarction, sudden cardiac death, arrhythmia, pulmonary embolism, bowel or limb infarction, or any death not readily attributable to a non-ischemic cause
Hemorrhagic Vascular death	Death due to intracranial or systemic hemorrhage

*Appendix 2: modified Rankin Scale*

The modified Rankin Scale (mRS) is a scale commonly used for measuring the degree of disability or dependence in the daily activities of individuals who have suffered a stroke, and it has become the most widely used clinical outcome measure for stroke clinical trials.	
Description	Score (select one)
No symptoms at all	0 
No significant disability despite symptoms; able to carry out all usual duties	1 

and activities	
Slight disability; unable to carry out all previous activities, but able to look after own affairs without assistance	2 
Moderate disability; requiring some help, but able to walk without assistance	3 
Moderately severe disability; unable to walk without assistance and unable to attend to own bodily needs without assistance	4 
Severe disability; bedridden, incontinent and requiring constant nursing care and attention	5 

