## **2 BACKGROUND AND RATIONAL**

### **2.1 The burden of acute non-disabling cerebrovascular event in China**

China bears the biggest burden of cerebrovascular diseases in the world, not only because of its huge population but also the propensity for cerebrovascular diseases; the number of patients who die from cerebrovascular diseases is more than three times that from cardiovascular diseases .

Acute non-disabling cerebrovascular event, including transient ischemic attack (TIA), defined as a mini-stroke that symptoms last less than 24 hours, and acute ischemic minor stroke, defined as an ischemic stroke with NIH Stroke Scale score  $\leq 3$ , is common and often a precursor of a disabling stroke. Ischemic cerebrovascular event i.e. ischemic stroke (IS) and TIA became the predominant cerebrovascular diseases subtype, it was estimated that over 2 million new stroke events occurred each year in China , and data from the China National Stroke Registry (CNSR), a national hospital-based registry across China showed that there were about 65% patients with ischemic stroke, and of these, more than 10% were minor ischemic stroke (unpublished data). So far it has not been reported about the incidence of TIA in China. The incidence of TIA in the United States (US) was approximately 68 per 100,000 to 86 per 100,000 person-years, corresponding to about 300,000 TIAs diagnosed each year . Based on the epidemiological studies in the US, it was estimated that at least 2million new TIA events would be diagnosed each year in China. What is more worrying about is that the incidence and mortality of stroke in the western country were declined yearly since the late 20th century, whereas ischemic stroke has been increasing annually and becomes the second leading cause of death in China. 

In addition, recurrence of stroke and other vascular events in patients with an initial acute nondisabling cerebrovascular event is one of the most frustrating medical situations.  Several cohort studies have shown that early (3 months) risk of stroke following index transient ischemic attack (TIA) and minor ischemic stroke is much higher than previously

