#### 4.6.3.4 Safety Endpoint

##### 4.6.3.4.1 Primary safety endpoints

- ✧ Incidence of severe bleeding or moderate bleeding (GUSTO definition, see appendix 6), including fatal bleeding and symptomatic intracranial hemorrhage

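### Appendix 1 of the final protocol and SAP: the intracranial hemorrhage classes contradict the hemorrhagic stroke definition and leave out non-fatal symptomatic bleeds with an NIHSS rise under 4

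*Supplement*

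**What the plan says.** Five entries in Appendix 1 of the final protocol bear on this.

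- Hemorrhagic stroke, a component of the primary endpoint: "An acute extravasation of blood into the brain parenchyma or subarachnoid space with associated neurological symptoms". There is no NIHSS threshold.
- Symptomatic intracerebral hemorrhage: a parenchymal bleed must be "associated with clinical deterioration, as defined by an increase of 4 points or more in the score on the NIHSS". A fatal bleed is the alternative route into this class.
- Asymptomatic intracerebral hemorrhage: "an acute extravasation of blood into the brain parenchyma without clinical deterioration".
- Other symptomatic intracranial hemorrhage: the same 4-point-or-death rule, with blood in the "subarachnoid space, epidural space, or subdural space with associated symptoms".
- Other asymptomatic intracranial hemorrhage: "An acute extravasation of blood into the subarachnoid space, epidural space, or subdural space without associated symptoms".

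Appendix 1 of the final SAP repeats the four hemorrhage classes but has no entry for hemorrhagic stroke.

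The classes feed the safety endpoints. Section 4.6.3.4.1 of the final protocol makes GUSTO severe or moderate bleeding the primary safety endpoint, "including fatal bleeding and symptomatic intracranial hemorrhage". The secondary safety endpoint is the 3-month incidence of intracranial hemorrhage, symptomatic and asymptomatic. The SAP's Safety Endpoint section lists both again.

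**The concern.** A symptomatic and an asymptomatic class should between them hold every bleed once, and neither should contradict the stroke endpoint. Here the symptomatic side is defined by a neurological score or death. The asymptomatic side is defined in one compartment by the absence of deterioration and in the others by the absence of symptoms. Hemorrhagic stroke is defined by the presence of symptoms. With these different yardsticks, one patient can carry two incompatible labels or none.

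Intracranial hemorrhage is a named safety objective (final protocol 3.2.5 and 3.2.12), and few such events are to be expected: section 2.2.4.3 reports two in 392 patients in the acute pilot trial, both on the combination. At counts of that order, one or two misfiled bleeds can change how the harm of the regimen reads. The efficacy and safety tables would also disagree about the same patient, and adjudicators working from different language versions could file that patient differently.

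**Working it through.** No sample size, power or alpha depends on these definitions, so the check is to run cases through the wording. Three sites were taken (parenchymal, subarachnoid, subdural or epidural). Each was combined with six profiles: no symptoms; symptoms with a rise of 0, 2, 3 or 4 in a survivor; and symptoms with a rise of 2 in a patient who dies of the bleed. That gives 3 × 6 = 18 cases.

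**Cases that work.** A bleed without symptoms falls in the asymptomatic class for its site. A symptomatic bleed with a rise of 4, or a fatal one, falls in the symptomatic class for its site. This covers 3 × 3 = 9 cases.

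**Cases that do not.** These are survivors with symptoms and a rise of 0, 2 or 3, the other 3 × 3 = 9 cases. The result is the same for all three rises:

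| Site | Hemorrhagic stroke (primary endpoint) | Symptomatic class | Asymptomatic class, English protocol and SAP | Asymptomatic class, Chinese protocol | GUSTO severe, English protocol |
|---|---|---|---|---|---|
| Parenchymal | Yes | No | Yes | Yes | Yes |
| Subarachnoid | Yes | No | No | Yes | Yes |
| Subdural or epidural | No | No | No | Yes | Yes |

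The 9 of 18 is a count of constructed cases, not a frequency.

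**Row 1 is a contradiction.** New arm weakness with a 3-point rise makes the bleed a hemorrhagic stroke. The rise is below the threshold that defines clinical deterioration, so the bleed is also an asymptomatic intracerebral hemorrhage. If deterioration is instead read in its everyday sense in the asymptomatic entry, the patient leaves that class but still does not reach the symptomatic one. The contradiction then becomes a gap.

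**Rows 2 and 3 are a gap in the English text.** The patient has symptoms, so cannot be in the asymptomatic class, and has not risen 4 points or died, so cannot be in the symptomatic one. Headache alone is enough to cause this if it counts as an associated symptom, because no NIHSS item in Appendix 3 scores it. The secondary safety endpoint is built from the two classes and misses the patient.

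**Language versions.** The Chinese final protocol's endpoint table defines the other asymptomatic class by the absence of neurological deterioration. It has no gap, but it labels the same symptomatic patients asymptomatic. It also files hemorrhagic transformation of an infarct under infarction, which the English entry does not say, so in Chinese the row 1 conflict concerns parenchymal bleeds other than transformation.

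**The case against.** The strongest reply is that little is lost. Four parts of it stand.

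- Hemorrhagic stroke has no NIHSS threshold, so the primary efficacy count is untouched. A subarachnoid bleed with neurological symptoms stays in it.
- GUSTO severe bleeding in the English Appendix 6 takes any documented intracranial hemorrhage, with no condition on symptoms or score. A reader might infer that the subdural patient is counted nowhere. The documents do not support that: the patient is in the English primary safety endpoint.
- The secondary safety endpoint takes both kinds of bleed, so a mislabeled parenchymal bleed stays in the total and only its sub-label is wrong.
- A 4-point threshold is a legitimate severity cut, and choosing it is no error.

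Three further inferences are tempting and should not be drawn. First, that the low entry score causes the problem: minor stroke is "acute ischemic minor stroke, defined as an ischemic stroke with NIH Stroke Scale score" of 3 or less, but a 4-point rise is attainable from there, and the mismatch would arise at any entry score. Second, that the Chinese GUSTO table drops these patients from the primary safety endpoint: it attaches a symptom condition only to post-traumatic intracranial bleeds, so trauma would have to be added to the case. Third, that symptomatic hemorrhage is understated by some given fraction: the documents contain nothing on how NIHSS changes are distributed after a bleed.

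The reply does not remove the defect. The fault lies in the partner classes and their conflict with hemorrhagic stroke, not in the threshold.

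**Conclusion.** The point holds within limits. As written, the rules mislabel non-fatal symptomatic parenchymal bleeds with a rise under 4. In the English protocol and the SAP they also omit the corresponding subarachnoid, subdural and epidural bleeds from a named secondary safety endpoint. Only the subdural and epidural ones lack any Appendix 1 category. The damage is confined to the split between symptomatic and asymptomatic bleeds and to the completeness of that one endpoint.

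The size cannot be stated. It is the number of survivors with a symptomatic bleed below the threshold, which the documents do not let one estimate.

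The conclusion assumes that events are classified by Appendix 1 as printed. Overt bleeds go to an independent adjudication committee whose charter is not among the documents. The charter might settle these cases, but nothing in the protocol or SAP says that it does.

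**What to change.** Rewrite the hemorrhage entries so that every bleed proven by imaging, surgery or autopsy falls in exactly one class, by the same rule in every compartment. Give no adjudicated hemorrhagic stroke the asymptomatic label. One workable layout keeps the 4-point rule and reports three rows:

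1. a rise of 4 points or more, or death from the bleed;
2. symptoms attributed to the bleed, below that threshold;
3. no symptoms.

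Add the hemorrhagic stroke definition to Appendix 1 of the SAP, and carry identical wording through the English protocol, the SAP and the Chinese protocol.

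The cost is text in the appendices and on the adjudication form. No sample size, visit or treatment changes. The downside is that the reported count of symptomatic, or of total, intracranial hemorrhage may come out slightly higher.

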Appendix 3: NIH Stroke Scale

Administer stroke scale items in the order listed. Record the performance in each category after each subscale exam. Do not go back and change scores. Follow directions provided for each exam technique. Scores should reflect what the patient does, not what the clinician thinks the patient can do. The clinician should record answers while administering the exam and work quickly. Except where indicated, the patient should not be coached (i.e., repeated requests to patient to make a special effort).

Instructions	Scale Definition	Score

1a. Level of Consciousness: The investigator must choose a response if a full evaluation is prevented by such obstacles as an endotracheal tube, language barrier, orotracheal trauma/bandages. A 3 is scored only if the patient makes no movement (other than reflexive posturing) in response to noxious stimulation.
	
0 = Alert; keenly responsive.
 
1 = Not alert; but arousable by minor stimulation to obey, answer, or respond.
 
2 = Not alert; requires repeated stimulation to attend, or is obtunded and requires strong or painful stimulation to make movements (not stereotyped).
 
3 = Responds only with reflex motor or autonomic effects or totally unresponsive, flaccid, and flexic.
	_____

Instructions	Scale Definition	Score

1b. LOC Questions: The patient is asked the month and his/her age. The answer must be correct - there is no partial credit for being close. Aphasic and stuporous patients who do not comprehend the questions will score 2. Patients unable to speak because of endotracheal intubation, orotracheal trauma, severe dysarthria from any cause, language barrier, or any other problem not secondary to aphasia are given a 1. It is important that only the initial answer be graded and that the examiner not "help" the patient with verbal or non-verbal cues.
	
0 = Answers both questions correctly.            1 = Answers one question correctly.            2 = Answers neither question correctly.
	
_____


1c. LOC Commands: The patient is asked to open and close the eyes and then to grip and release the non-paretic hand. Substitute another one step command if the hands cannot be used. Credit is given if an unequivocal attempt is made but not completed due to weakness. If the patient does not respond to command, the task should be demonstrated to him or her (pantomime), and the result scored (i.e., follows none, one or two commands). Patients with trauma, amputation, or other physical impediments should be given suitable one-step commands. Only the first attempt is scored.
	
0 = Performs both tasks correctly.            1 = Performs one task correctly.            2 = Performs neither task correctly.
	
_____

2. Best Gaze: Only horizontal eye movements will be tested. Voluntary or reflexive (oculocephalic) eye movements will be scored, but caloric testing is not done. If the patient has a conjugate deviation of the eyes that can be overcome by voluntary or reflexive activity, the score will be 1. If a patient has an isolated peripheral nerve palsy (CN III, IV or VI), score a 1. Gaze is testable in all aphasic patients. Patients with ocular trauma, bandages, pre-existing blindness, or other disorder of visual acuity or fields should be tested with reflexive movements, and a choice made by the investigator. Establishing eye contact and then moving about the patient from side to side will occasionally clarify the presence of a partial gaze palsy.
	
0 = Normal.            1 = Partial gaze palsy; gaze is abnormal in one or both eyes, but forced deviation or total gaze paresis is not present.            2 = Forced deviation, or total gaze paresis not overcome by the oculocephalic maneuver.
	
_____


3. Visual: Visual fields (upper and lower quadrants) are tested by confrontation, using finger counting or visual threat, as appropriate. Patients may be encouraged, but if they look at the side of the moving fingers appropriately, this can be scored as normal. If there is unilateral blindness or enucleation, visual fields in the remaining eye are scored. Score 1 only if a clear-cut asymmetry, including quadrantanopia, is found. If patient is blind from any cause, score 3. Double simultaneous stimulation is performed at this point. If there is extinction, patient receives a 1, and the results are used to respond to item 11.
	
0 = No visual loss.            1 = Partial hemianopia.            2 = Complete hemianopia.            3 = Bilateral hemianopia (blind including cortical blindness).
	
_____

Instructions	Scale Definition	Score

4. Facial Palsy: Ask – or use pantomime to encourage – the patient to show teeth or raise eyebrows and close eyes. Score symmetry of grimace in response to noxious stimuli in the poorly responsive or non-comprehending patient. If facial trauma/bandages, orotracheal tube, tape or other physical barriers obscure the face, these should be removed to the extent possible.
	
0 = Normal symmetrical movements.
 
1 = Minor paralysis (flattened nasolabial fold, asymmetry on smiling).
 
2 = Partial paralysis (total or near-total paralysis of lower face).
 
3 = Complete paralysis of one or both sides (absence of facial movement in the upper and lower face).
	
_____


5. Motor Arm: The limb is placed in the appropriate position: extend the arms (palms down) 90 degrees (if sitting) or 45 degrees (if supine). Drift is scored if the arm falls before 10 seconds. The aphasic patient is encouraged using urgency in the voice and pantomime, but not noxious stimulation. Each limb is tested in turn, beginning with the non-paretic arm. Only in the case of amputation or joint fusion at the shoulder, the examiner should record the score as untestable (UN), and clearly write the explanation for this choice.
	
0 = No drift; limb holds 90 (or 45) degrees for full 10 seconds.
 
1 = Drift; limb holds 90 (or 45) degrees, but drifts down before full 10 seconds; does not hit bed or other support.
 
2 = Some effort against gravity; limb cannot get to or maintain (if cued) 90 (or 45) degrees, drifts down to bed, but has some effort against gravity.
 
3 = No effort against gravity; limb falls.
 
4 = No movement.
 
UN = Amputation or joint fusion, explain: _____
 
5a. Left Arm
 
5b. Right Arm
	
_____
 
_____

Instructions	Scale Definition	Score

6. Motor Leg: The limb is placed in the appropriate position: hold the leg at 30 degrees (always tested supine). Drift is scored if the leg falls before 5 seconds. The aphasic patient is encouraged using urgency in the voice and pantomime, but not noxious stimulation. Each limb is tested in turn, beginning with the non-paretic leg. Only in the case of amputation or joint fusion at the hip, the examiner should record the score as untestable (UN), and clearly write the explanation for this choice.
	
0 = No drift; leg holds 30-degree position for full 5 seconds.
 
1 = Drift; leg falls by the end of the 5-second period but does not hit bed.
 
2 = Some effort against gravity; leg falls to bed by 5 seconds, but has some effort against gravity.
 
3 = No effort against gravity; leg falls to bed immediately.
 
4 = No movement.
 
UN = Amputation or joint fusion, explain: _____
 
6a. Left Leg
 
6b. Right Leg
	
_____
 
_____


7. Limb Ataxia: This item is aimed at finding evidence of a unilateral cerebellar lesion. Test with eyes open. In case of visual defect, ensure testing is done in intact visual field. The finger-nose-finger and heel-shin tests are performed on both sides, and ataxia is scored only if present out of proportion to weakness. Ataxia is absent in the patient who cannot understand or is paralyzed. Only in the case of amputation or joint fusion, the examiner should record the score as untestable (UN), and clearly write the explanation for this choice. In case of blindness, test by having the patient touch nose from extended arm position.
	
0 = Absent.
 
1 = Present in one limb.
 
2 = Present in two limbs.
 
UN = Amputation or joint fusion, explain: _____
	
_____

8. Sensory: Sensation or grimace to pinprick when tested, or withdrawal from noxious stimulus in the obtunded or aphasic patient. Only sensory loss attributed to stroke is scored as abnormal and the examiner should test as many body areas (arms [not hands], legs, trunk, face) as needed to accurately check for hemisensory loss. A score of 2, "severe or total sensory loss," should only be given when a severe or total loss of sensation can be clearly demonstrated. Stuporous and aphasic patients will, therefore, probably score 1 or 0. The patient with brainstem stroke who has bilateral loss of sensation is scored 2. If the patient does not respond and is quadriplegic, score 2. Patients in a coma (item 1a=3) are automatically given a 2 on this item.
	
0 = Normal; no sensory loss.
 
1 = Mild-to-moderate sensory loss; patient feels pinprick is less sharp or is dull on the affected side; or there is a loss of superficial pain with pinprick, but patient is aware of being touched.
 
2 = Severe to total sensory loss; patient is not aware of being touched in the face, arm, and leg.
	
_____

Instructions	Scale Definition	Score

9. Best Language: A great deal of information about comprehension will be obtained during the preceding sections of the examination. For this scale item, the patient is asked to describe what is happening in the attached picture, to name the items on the attached naming sheet and to read from the attached list of sentences. Comprehension is judged from responses here, as well as to all of the commands in the preceding general neurological exam. If visual loss interferes with the tests, ask the patient to identify objects placed in the hand, repeat, and produce speech. The intubated patient should be asked to write. The patient in a coma (item 1a=3) will automatically score 3 on this item. The examiner must choose a score for the patient with stupor or limited cooperation, but a score of 3 should be used only if the patient is mute and follows no one-step commands.
	
0 = No aphasia; normal.
 
1 = Mild-to-moderate aphasia; some obvious loss of fluency or facility of comprehension, without significant limitation on ideas expressed or form of expression. Reduction of speech and/or comprehension, however, makes conversation about provided materials difficult or impossible. For example, in conversation about provided materials, examiner can identify picture or naming card content from patient's response.
 
2 = Severe aphasia; all communication is through fragmentary expression; great need for inference, questioning, and guessing by the listener. Range of information that can be exchanged is limited; listener carries burden of communication. Examiner cannot identify materials provided from patient response.
 
3 = Mute, global aphasia; no usable speech or auditory comprehension.
	
_____


10. Dysarthria: If patient is thought to be normal, an adequate sample of speech must be obtained by asking patient to read or repeat words from the attached list. If the patient has severe aphasia, the clarity of articulation of spontaneous speech can be rated. Only if the patient is intubated or has other physical barriers to producing speech, the examiner should record the score as untestable (UN), and clearly write an explanation for this choice. Do not tell the patient why he or she is being tested.
	
0 = Normal.
 
1 = Mild-to-moderate dysarthria; patient slurs at least some words and, at worst, can be understood with some difficulty.
 
2 = Severe dysarthria; patient's speech is so slurred as to be unintelligible in the absence of or out of proportion to any dysphasia, or is mute/anarthric.
 
UN = Intubated or other physical barrier, explain: _____ _____
	
_____

Instructions	Scale Definition	Score

11. Extinction and Inattention (formerly Neglect): Sufficient information to identify neglect may be obtained during the prior testing. If the patient has a severe visual loss preventing visual double simultaneous stimulation, and the cutaneous stimuli are normal, the score is normal. If the patient has aphasia but does appear to attend to both sides, the score is normal. The presence of visual spatial neglect or anosagnosia may also be taken as evidence of abnormality. Since the abnormality is scored only if present, the item is never untestable.
	
0 = No abnormality.
 
1 = Visual, tactile, auditory, spatial, or personal inattention or extinction to bilateral simultaneous stimulation in one of the sensory modalities.
 
2 = Profound hemi-inattention or extinction to more than one modality; does not recognize own hand or orients to only one side of space.
	
_____

	
Total NIHSS:
	
_____

